Based on the aforementioned safety margins, the starting dose for this phase 1 study will be 3 mg/kg AK1967, administered as a single infusion over 2 hour. This dose should be increased up to a maximum of 12 mg/kg, to provide a sufficient safety margin for the intended therapeutic dose of 5-10 mg/kg. As the actual body weight might be difficult to acquire in critically ill patients, and a slightly higher dose for a later treatment may turn out to be more beneficial, 12 mg/kg provides a sufficient safety window. The intended maximum dose of 12 mg/kg still provides a 13- and 29-fold safety margin to the observed NOAELs of the GLP-toxicity studies (table 3).

f. Pharmacokinetic considerations

From preclinical animal studies, it is known that AK1967 has a short half-life compared to other IgG1 antibodies (see GLP-toxicity studies, section 4.3 of the IB). This shorter half-life also results in a reduced time-range of relevant pharmacodynamic effects compared to other antibodies, with animal disease models demonstrating therapeutic effects in a 24-48 hour time-window (see relevant studies in IB section 4.1.1). The administration of the AK1967 antibody is not associated with the occurrence of any toxic or active metabolites.

g. Predictability of effect

Prior to performing preclinical experiments with AK1967, luminometric immunoassays (LIA) for cDPP3 concentration quantification and fluorescence assays for cDPP3 activity quantification were already developed (13) (see IB section 4.2.1 for reference assays 080-06000/03, 02-16-03 and 02-16-02). These assays allow for the accurate quantification of cDPP3 enzyme activity, both under baseline circumstances as well as during different critical illness etiologies. The availability of enzyme activity assays allows for an additional method to monitor AK1967's pharmacokinetic (and -dynamic) effects, because the dose-dependency of its enzyme-inhibitory potential can be quantified with relative ease. Thus, these assays will serve as additional (secondary) measures of AK1967's pharmacokinetic properties.

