13. STATISTICAL ANALYSIS

13.1 Description of statistical methods

Parameters will be presented as mean ± SEM or median and interquartile ranges, depending on their distribution. Categorical data will be presented as counts and percentages. A two sided p-value <0.05 is considered significant. Statistical analyses will be performed with R (http://www.r-project.org). No interim analyses will be performed during the study protocol.

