Fili	ng: h	ttps:/	/fourteenfour.dhcvisioncloud.com/dhcvision/document.jsp?key=DATABASE:1001;IO:1527897	Page 1 of 22	

Form printed on

Form FB_00079_Statistical Analysis Plan

Form Valid From: 08/03/2024

Form Version: 1

Record Title:

Record Title: Clinical Statistical Analysis Plan CT-P1-001

	8.6	Analysis of secondary endpoints	15
	Des	scriptive pharmacokinetic analyses	16
	8.7	Additional analyses	18
9	Cor	ntents of statistical tables and figures	19

Form Valid From: 08/03/2024

Form Version: 1

Record Title:

Record Title: Clinical Statistical Analysis Plan CT-P1-001

1 Background and scope

This SAP is created for the study and protocol as stated below:

Table 1 Basic trial information.

EU-CT number	2023-507035-37-00	
Trial name	Not applicable	
Clinical Trial Protocol Version	Latest Version 5	

All abbreviations are included in the Glossary

The following documents are attached to the QM record of this SAP:

- None (the Data Review Plan and Report are referenced in DHC VISION)

2 Study objectives

The objective of the AK1967 Phase 1 study is to evaluate the safety and tolerability of single escalating doses of AK1967 in healthy male volunteers. Main trial endpoints associated with this objective are fully described in the study protocol. To summarize, endpoints for this safety outcome are defined as differences between the different AK1967 dosage groups and the placebo group in:

- Reported number of adverse events after IMP administration
- Kinetics of vital signs at baseline and following IMP administration
- Local tolerability at site of IMP infusion
- Safety laboratory parameters at baseline and following IMP administration
- 12-lead electrocardiogram (ECG) parameters at baseline and following IMP administration

There are several secondary trial objectives. A full overview is again provided in the study protocol. To summarize, secondary trial measurements/endpoints discussed in this document include:

- Pharmacokinetics of the IMP (including AUC, C_{max} , Terminal $T_{1/2}$, clearance, VD)
- Pharmacodynamics (enzyme activity and concentration of DPP3) at baseline and following IMP administration.
- Pharmacodynamics related to the renin-angiotensin system (blood plasma levels of renin-angiotensin system metabolites) at baseline and following IMP administration
- Pharmacodynamics related to catecholamines (blood plasma levels of adrenergic metabolites) at baseline and following IMP administration

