8.2 Definitions, derived variables and handling of missing data

Definitions of time points / time windows

Baseline will be defined per parameter and will be the value/measurement at the following timepoints:

Parameter for	Timepoint
Demographics	Screening
Vital signs	Baseline (before IMP administration)
ECG	Baseline (Screening)
Local laboratory assessment	Baseline (before IMP administration)
Arterial blood gas analysis	Baseline (before IMP administration)

Filing: https://fourteenfour.dhcvisioncloud.com/dhcvision/document.jsp?key=DATABASE:1001;IO:1527897	Page 11 of 22
---	---------------

Form Valid From: 08/03/2024

Form Version:

Record Title:

Record Title: Clinical Statistical Analysis Plan CT-P1-001

Parameter for	Timepoint
Biomarker (DPP3 concentration and	Baseline (before IMP administration)
activity)	

Derived variables

Extent of exposure:

Extent of exposure will be defined as total exposure in mg and calculated as:

total exposure
$$[mg] = 20 \frac{mg}{ml} * IMP volume [ml] * factor$$

where IMP volume is the body weight adjusted IMP volume before addition of NaCl and factor equals 1 for treatment group 12 mg/kg AK1967, 1/2 for treatment group 6 mg/kg AK1967, and 1/4 for treatment group 3 mg/kg AK1967. Total exposure will not be calculated for the Placebo treatment group.

In case of premature termination of the infusion, total exposure will additionally be multiplied by $\frac{volume\ administered\ [ml]}{c}$ in order to account for only partly administration of study drug.

Exposure per kg body weight will be calculated as:

Exposure per kg body weight
$$\left[\frac{mg}{kg}\right] = \frac{total\ exposure\ [mg]}{body\ weight\ [kg]}$$

Body mass index (BMI):

$$BMI = \frac{Weight [kg]}{Height [m]^2}$$

Handling of missing values

Data from subjects who prematurely terminate the trial will be used to the maximum possible extent. Missing values will not be inputted.

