Data distribution for all pharmacodynamic biomarkers will be evaluated using the Kolmogorov-Smirnov test and normal/non-normal distribution will be reported. All variables will be expressed both as mean ± standard deviation (SD), as well as medians and interquartile ranges (IQR) in tables and graphical representations of the data. In case a value of one of these parameters is an outlier in a subject, this will be described separately. Between group differences in pharmacodynamic biomarkers will be assessed using one-way-RM-ANOVA tests (for normally distributed data), or Kruskal-Wallis tests (for non-normally distributed data). In case of a p-value of <0.05 for these tests (implying the presence of dosage groups with differences in a vital sign at a specific timepoint), subsequent Bonferroni or Mann-Whitney-U post-hoc tests will be performed (depending on data distribution), to assess which subgroups are different, and in what direction.

Form Valid From: 08/03/2024

Form Version: 1

Record Title: Clinical Statistical Analysis Plan CT-P1-001

Record Title:

Additional analyses related to the effects of AK1967 on safety endpoints

Between group differences in vital signs will be assessed using one-way-RM-ANOVA tests (for normally distributed data), or Kruskal-Wallis tests (for non-normally distributed data). In case of a p-value of <0.05 for these tests (implying the presence of dosage groups with differences in a vital sign at a specific timepoint, subsequent Bonferroni or Mann-Whitney-U post-hoc tests will be performed (depending on data distribution), to assess which subgroups are different, and in what direction.

Between group differences over time for vital signs, safety laboratory and inflammatory parameters (i.e. laboratory/inflammatory parameter changes during the course of the experimental protocol) will be analyzed using two-way-RM-ANOVA tests (for normally distributed data), or two-way-RM-ANOVA tests on ranked transformed data (for non-normally distributed data). Both tests will report the time*group interaction term to establish significance, which will be defined as p <0.05.

9 Contents of statistical tables and figures

	14 Tables and figures referred to but not included in the text	

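### For safety laboratory parameters, SAP 8.7 rests significance on the time*group interaction alone, a weak test for a moderate sustained shift and a blind one if the pre-dose value is not a time level

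*SAP*

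**What the plan says.** SAP section 2 states the safety aim as a contrast between groups: "endpoints for this safety outcome are defined as differences between the different AK1967 dosage groups and the placebo group in" a list that includes the laboratory parameters.

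The test is in the last paragraph of SAP 8.7. It covers "Between group differences over time for vital signs, safety laboratory and inflammatory parameters" and uses "two-way-RM-ANOVA tests (for normally distributed data), or two-way-RM-ANOVA tests on ranked transformed data (for non-normally distributed data"). It then names the deciding term: "Both tests will report the time*group interaction term to establish significance, which will be defined as p <0.05". Protocol 13.1 sets the same threshold: "A two sided p-value <0.05 is considered significant".

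The three kinds of parameter in that paragraph are not treated alike elsewhere in the SAP:

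- **Vital signs** have a separate between-group test in the preceding paragraph of 8.7.
- **Inflammatory cytokines** are listed among the pharmacodynamic aims of SAP 8.6, which tests group differences by one-way repeated-measures ANOVA or Kruskal-Wallis. The 8.6 subsection title omits them, but the output list in SAP section 9 also places inflammatory mediators with the pharmacodynamic outputs.
- **Safety laboratory parameters** have only the interaction. The Kruskal-Wallis comparison planned under demographic data and baseline characteristics concerns baseline values.

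The scope is given as "laboratory/inflammatory parameter changes during the course of the experimental protocol". SAP 8.2 fixes which measurement is the baseline ("Baseline will be defined per parameter and will be the value/measurement at the following timepoints"). Neither place says whether that value enters the ANOVA as a level of time, or whether raw values or changes from baseline are modelled.

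**The concern.** The question is whether dosed men differ from placebo. The interaction tests another null hypothesis: that the four group profiles over time are parallel. A shift that starts early and persists makes the profiles non-parallel only at the step from the pre-dose value to the first post-dose value. That single contrast is then averaged with many time contrasts that carry no signal. If the pre-dose value is left out of the time factor, the post-dose profiles are parallel and nothing remains to detect. Modelling changes from baseline over the post-dose times has the same result, because subtracting a constant from each subject does not alter the interaction.

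At stake is how a non-significant result is read. The SAP attaches significance to this one term, so a moderate lasting change in a laboratory value could be summarised as no significant group difference over time.

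**Working it through.** **The plan's own figures.** The documents give no power, effect size or SD for these tests, so there is no power figure to reproduce. The group sizes agree: 3 × (6 + 2) = 24, that is 6 per dose and 6 pooled placebo.

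**Inputs from the documents.** G = 4 groups, n = 6, α = 0.05. Protocol Table 8 gives haematology and biochemistry at baseline, 30, 60, 120, 240, 360 and 600 minutes and 24 hours, so K = 8. Clotting lacks the 30-minute sample (K = 7). With the six follow-up visits, haematology and biochemistry have K = 14.

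**Assumptions.** Normal, complete data; compound symmetry with within-subject correlation ρ of 0.5, 0.7 or 0.9; σ = 1; an equal shift δ in all three dose groups. With effects (0, 1, 1, 1) and mean 0.75, S = Σ(d_g − d̄)² = 0.5625 + 3 × 0.0625 = 0.75 for δ = 1.

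**Interaction, pre-dose value as a time level.** Degrees of freedom are 3(K−1) = 21 and 20(K−1) = 140. For a step at the first post-dose sample, λ = n·S·[(K−1)/K]/(1−ρ) = 6 × 0.75 × 0.875/(1−ρ) = 3.9375/(1−ρ).

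**ANCOVA of the mean post-dose value on the pre-dose value.** Degrees of freedom are 3 and 19. Residual variance v = [1+(K−2)ρ]/(K−1) − ρ², and λ = n·S/v = 4.5/v. Chance baseline imbalance lowers power slightly below this formula, so the table gives simulated values (4,000 runs per case).

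| ρ, δ = 1, step | λ interaction | power | with Greenhouse-Geisser | v | λ ANCOVA | power |
|---|---|---|---|---|---|---|
| 0.5 | 7.9 | 27% | 20% | 0.321 | 14.0 | 80% |
| 0.7 | 13.1 | 47% | 38% | 0.253 | 17.8 | 89% |
| 0.9 | 39.4 | 97% | 95% | 0.104 | 43.2 | >99% |

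At δ = 1.5, S is multiplied by 2.25, and interaction power becomes 63% (ρ = 0.5) and 90% (ρ = 0.7).

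**A comparison that does not depend on ρ.** For a step, one-way ANOVA of the mean post-dose change from baseline has the same λ as the interaction but only 3 and 20 df. Where that test has 80% power, the interaction has 47% at K = 8 and 35% at K = 14. This loss is due purely to the numerator degrees of freedom.

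**Effect building up over the infusion.** With 0.25, 0.5 and 1 of the shift at 30, 60 and 120 minutes and 1 thereafter, δ = 1:

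| ρ | interaction | with Greenhouse-Geisser | ANCOVA |
|---|---|---|---|
| 0.5 | 38% | 29% | 60% |
| 0.7 | 64% | 54% | 72% |
| 0.9 | >99% | 99% | 99% |

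**Pre-dose value not a time level, step with δ = 1.** The interaction rejects in about 5% of runs (3% corrected) at every ρ, which is the rate under no effect. ANCOVA keeps the step-table power.

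**Short transient at 2 to 4 hours.** The order reverses: 39-75% for the corrected interaction against 12-13% for ANCOVA.

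**Raw group main effect as the added term (K = 8, δ = 1, step).** It has 44%, 35% and 28% at ρ = 0.5, 0.7 and 0.9, against 27%, 47% and 97% for the interaction. It is not a dependable substitute, because it averages in the unaffected baseline and does not remove between-subject variance.

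**The case against.** The strongest reply is that little hangs on this test. It sits under additional analyses. Protocol 13.6.2 calls the repeated-measures ANOVA exploratory and optional and lists other group tests for continuous variables. Protocol 13.5 and SAP 3.1 plan no comparative analysis of the primary safety endpoint. SAP 8.5 gives changes from baseline by group and time point, marks out-of-range values and tabulates categorised changes. A sustained shift would be visible there, and nothing says that a non-significant interaction will be reported as no effect. All of this stands and limits the consequence. It does not explain why laboratory parameters alone lack a between-group test in the SAP.

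A second reply is that the choice of test is a trade-off between effect shapes. This also stands: the interaction is better for transient effects and comes close to the ANCOVA for a gradual onset at higher correlation. It is a reason to keep the interaction, not to rely on it alone.

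Four stronger readings are tempting, and the documents do not support them:

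- **The gap covers inflammatory parameters and vital signs too.** Cytokines come under the group test of SAP 8.6, and vital signs have their own test in 8.7.
- **Sustained effects are mostly missed.** That fails for larger shifts or high within-subject correlation, and the documents give neither quantity.
- **The protocol expects this effect shape.** Section 3.1(f) says "with animal disease models demonstrating therapeutic effects in a 24-48 hour time-window". That describes therapeutic effects in diseased animals, in a sentence about a shortened duration of action. It does not predict laboratory changes in healthy men.
- **The pre-dose value is excluded from the time factor.** The SAP does not say so; it is silent.

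**Conclusion.** The point holds for safety laboratory parameters, as an improvement to an exploratory analysis. The interaction is the only term the SAP names for them. For a sustained 1-SD step with ρ of 0.5 to 0.7, it has roughly one third to one half of the power of a baseline-adjusted comparison of the same data. The shortfall is smaller for a gradual onset and nearly gone at ρ = 0.9. The unstated role of the pre-dose value matters more, because one permissible reading leaves the test with no power against a constant post-dose shift of any size.

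The percentages rest on assumed effect size, effect shape, correlation structure and normality. The degrees of freedom and the blindness without a baseline level do not depend on the assumed effect size or correlation.

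**What to change.** In SAP 8.7:

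1. State that the pre-dose value is a level of time in the two-way repeated-measures ANOVA.
2. For each safety laboratory parameter, add the group effect on the mean post-dose treatment-day value adjusted for the pre-dose value (ANCOVA or the equivalent mixed-model contrast), with estimates and 95% confidence intervals for each dose against placebo.
3. Keep the interaction for transient effects.
4. State that a non-significant interaction alone is not reported as absence of a group difference.
5. Reconcile 8.6 and 8.7 for inflammatory cytokines, say which between-group test applies, and apply item 2 to them as well.

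The added term should be baseline-adjusted; the raw group main effect from the same ANOVA would not serve. No split of the 0.05 level is needed, since both terms are exploratory and should be labelled so.

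The cost is SAP wording plus one more exploratory model and p-value per parameter, from data already collected. The extra p-values add to the chance findings to be expected, which is a reason to lead with the estimates and intervals.

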13.6.2 Analysis secondary endpoint(s)

Pharmacokinetics of Procizumab (including AUC, C_{max} , terminal $t_{1/2}$, Cl, V) will be determined for each dose and overall. Changes over time in blood plasma levels and activity of cDPP3 and other variables (vital signs, laboratory parameters, ECG, angiotensin metabolites, cytokines) within each treatment group will be described and plotted. They may be analyzed exploratory (within or between groups) by repeated measures one- or two-way analysis of variance. Data will be log-transformed if necessary.

Differences between subjects will be analyzed using Chi² tests or Fisher exact tests for counts (e.g. adverse events). T-tests, Mann-Whitney-U tests, one- or two-way analyses of variance tests or Kruskal-Wallis tests will be implemented for continuous variables, with the choice of test depending on the number of groups compared, as well as the data's distribution.

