3.1 Sample size determination / power analysis

As the primary endpoint is safety and no comparative statistical analyses will be performed on this endpoint, a sample size calculation is not warranted. A generally accepted group size (for dose escalating phase 1 studies) of 6 subjects per dosing group will be included (in addition to the 2 placebo-treated subjects per dosing group, also resulting in a total of 6 in the placebo-group). A sample size of 6 subjects per treatment group is regarded as being large enough to justify continuation of the trial with the next dosing group in the absence of relevant adverse events related to the study medication. Likewise, one or more severe or serious adverse events considered to be related to the study medication could be enough to discontinue the study without a statistical difference in (S)AEs between the groups.

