5.3 Endpoints for the exploratory objectives

Not applicable

6 General conventions

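### SAP 8.7 turns the protocol's optional, exploratory repeated-measures tests into mandatory tests that establish significance at p<0.05, over 27 to 40 parameters with no control across them

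*SAP*

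**What the plan says.** Protocol 13.6.2 covers changes over time in vital signs, laboratory parameters, cytokines and other variables. It says: "They may be analyzed exploratory (within or between groups) by repeated measures one- or two-way analysis of variance". The comparison is therefore permitted, not required, and it carries the exploratory label.

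SAP 8.7, under the part on safety endpoints, covers the same ground. "Between group differences over time for vital signs, safety laboratory and inflammatory parameters" are to be analysed by two-way repeated-measures ANOVA, on ranks if the data are not normal. It continues: "Both tests will report the time*group interaction term to establish significance, which will be defined as p <0.05". The text of 8.7 does not use the word exploratory. It names no leading parameter, order of testing or division of alpha. Bonferroni appears only as a post-hoc step between dose groups after a single omnibus test.

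Three other places bear on the point:

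- SAP 3.1, on the primary safety endpoint, says that "no comparative statistical analyses will be performed on this endpoint". Protocol 13.5 says the same.
- SAP 3.2 nevertheless states a null hypothesis for that endpoint, comparing all AK1967 doses combined with placebo.
- Protocol 13.1 sets a general convention: "A two sided p-value <0.05 is considered significant".

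**The concern.** Between protocol and SAP, an optional exploratory look has become a required test whose result is declared significant or not. The threshold applies separately to every parameter, so the chance of at least one false declaration grows with the number of parameters. The SAP neither limits that chance nor warns the reader of it.

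Vital signs and laboratory parameters are components of the primary safety endpoint; cytokines are a secondary endpoint. For the primary components, the SAP therefore says in 3.1 that no comparison will be made and in 8.7 that comparisons will be made and significance established.

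This is the first human study of AK1967. A laboratory value or vital sign reported as significantly different between dose groups could be carried forward as a drug effect when it is one of the chance results that a few dozen tests produce.

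**Working it through.** The documents state no family-wise error rate, so there is no figure of the plan's own to reproduce. The check counts the tests and works out the chance of at least one false result.

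**Number of interaction tests**

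| Family | Strict count | Upper count | Source |
|---|---|---|---|
| Vital signs | 4 | 6 | SAP 5.1 lists four; SAP 8.5 splits blood pressure into systolic, diastolic and mean |
| Safety laboratory | 19 | 25 | SAP 5.1 lists 19; Protocol section 4 adds LDH and albumin (21); counting the differential as five cell types adds 4 (assumption) |
| Inflammatory | 4 | 9 | SAP 5.2 names four; the footnotes to Protocol table 8 name nine |
| Total | 27 | 40 | |

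With the differential counted once, the fuller lists give 6 + 21 + 9 = 36. The separate one-way tests of vital signs in 8.7 are left out.

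**Independent tests, each at exactly 5%, no true effect:** chance of at least one p<0.05 = 1 − 0.95^m.

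- m = 27: 1 − 0.95^27 = 75.0%
- m = 36: 1 − 0.95^36 = 84.2%
- m = 40: 1 − 0.95^40 = 87.1%

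Expected false positives are 27 × 0.05 = 1.35 and 40 × 0.05 = 2.0. For the primary components alone (no cytokines), m runs from 4 + 19 = 23 to 6 + 25 = 31, which gives 69% to 80%.

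**Correlated tests.** The time*group F test was simulated with four groups of 6, no true effect, 8 time points, sphericity satisfied, and the same correlation between every pair of parameters (1,500 runs). The Monte Carlo standard error is at most √(0.25/1500) = 1.3 percentage points. The correlations are assumptions, because the documents give none.

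| Correlation between parameters | 27 tests | 40 tests |
|---|---|---|
| 0.3 | 67% | 76% |
| 0.5 | 50% | 63% |
| 0.7 | 37% | 44% |
| 0.8 | 30% | 31% |

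**Sensitivity to the 5% assumption.** The SAP names no sphericity correction. With 13 time points and serial correlation of 0.7 (AR(1), 800 runs), the uncorrected test rejects about 12% of the time per parameter. The chance of at least one false result at correlations 0.3, 0.5 and 0.7 is then:

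- uncorrected: 95%, 86% and 66% (40 tests); 92%, 77% and 63% (27 tests)
- with Greenhouse-Geisser, about 4% per test: 72%, 51% and 37% (40 tests); 58%, 45% and 32% (27 tests)

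**The case against.** The strongest reply is that the SAP already keeps these tests in a minor place. They sit under a heading for additional analyses. SAP 8.5 analyses the primary safety data descriptively, as Protocol 13.6.1 does. The output list in SAP section 9 plans only descriptive safety tables. The 0.05 convention is already in Protocol 13.1, and the second paragraph of Protocol 13.6.2 plans group tests without the word exploratory. All of that is correct, and it limits the consequence. It does not change the sentence in 8.7, which says the p-value establishes significance. A heading does not make a p-value nominal.

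Several stronger readings are tempting, and the documents do not support them:

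- *Vital signs are tested at every ten-minute interval.* SAP 8.7 names a one-way repeated-measures test. The clause about a specific timepoint is an aside that recurs, still referring to vital signs, in the pharmacodynamic text: "differences in a vital sign at a specific timepoint), subsequent Bonferroni or Mann-Whitney-U post-hoc tests will be performed". Ten-minute averaging is a correction for spurious readings, and SAP 8.5 summarises minimum and maximum vital signs by day. A plan for interval-by-interval testing cannot be inferred.
- *The heading "Endpoints for the exploratory objectives", marked not applicable, makes 8.7 confirmatory.* It says only that no exploratory endpoints are defined. It does not classify the tests in 8.7.
- *All the tested parameters are primary endpoints.* Cytokines are secondary in both documents, so SAP 3.1 does not cover them.
- *The plan cannot tell a false signal from a real one.* SAP 8.5 provides adverse-event relatedness, flagged out-of-range values, shifts to 1.5 and 2 times the upper limit of normal, fold-change categories and graded ECG interpretation.
- *Dose escalation could turn on a chance p-value.* SAP 3.1 and Protocol 13.5 rest continuation on related adverse events without requiring a statistical difference, and Protocol 12.10 gives the review to the DSMB. No stated decision uses an 8.7 p-value.

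**Conclusion.** The point holds as a conflict over the status of these tests. The SAP replaces the protocol's optional, exploratory analysis with a required test at full alpha on each of 27 to 40 parameters. For vital signs and laboratory parameters, this also contradicts SAP 3.1.

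The size depends on the correlation between parameters, which is not known. A reader might infer that a false significant result is always more likely than not. That holds for independent or weakly correlated parameters. At a correlation of 0.5 the strict count gives an even chance, and at 0.7 both counts fall below one half. Even at 0.8, about 30% is some six times the nominal 5%. All these figures assume no true drug effect. The main ones also assume that each test holds its 5%.

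The harm is confined to reporting: a chance difference may be labelled significant in the first human safety data. The primary descriptive analysis and the stated escalation rules are not affected.

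**What to change.** In SAP 8.7, replace the clause that makes the interaction term establish significance at p<0.05 with:

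> These analyses are exploratory, as in Protocol 13.6.2; p-values are nominal, unadjusted for the number of parameters tested, and will not on their own be reported as establishing a safety difference; the number of tests performed will be stated.

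Then reconcile 8.7 with SAP 3.1 and 3.2. Section 3.1 should say that the 8.7 tests are exploratory and are not the analysis of the primary endpoint. Section 3.2 should either drop its null hypothesis or state that no confirmatory test of it is planned.

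The cost is SAP wording. No data, listing or descriptive table is lost. The one real downside is that the report can no longer call a single safety p-value significant.
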